**REVISION HISTORY**

Revision #	Version Date	Summary of Changes	Consent Change?
1	7/11/19	Additional treatment task added and addition of community sample	No
2	7/30/19	Change in inclusion criteria and addition of behavioral tasks	Yes
3	9/12/19	Change in exclusion criteria, sample size, and questionnaires	Yes
4	7/17/20	Adapt study to be administered online, add study personnel, increase sample size	Yes
5	10/28/20	Change in cutoff for contacting people from mass screener for recruitment and addition of SONA screener for recruitment	No

## 1.0 Study Summary

Study Title	An Exposure-Based Treatment for Perfectionism
Study Design	Randomized Intervention Trial
Primary Objective	Evaluate the efficacy of an exposure-based treatment for perfectionism.
Secondary Objective(s)	Evaluate the effect of the treatment on depressive, anxiety, obsessive-compulsive, and eating disorder symptoms.
Research Intervention(s)	Exposure-Based Treatment for Perfectionism (see details below)
Study Population	FSU student subject pool participants and participants from the community
Sample Size	80
Study Duration for individual participants	2 weeks
Study Specific Abbreviations/ Definitions	Exposure-based perfectionism treatment (EPT)

## 2.0 Objectives\*

2.1 The purpose of this study is to test the efficacy of an exposure-based treatment for perfectionism. The aims of the study include:

- Evaluating whether a short-term computerized intervention can decrease perfectionism symptomatology (as measured by the Frost Multidimensional Perfectionism Scale (FMPS)).
- Seeing if this intervention also decreases levels of anxiety and depression, and possibly other symptoms related to obsessive-compulsive disorder (OCD) and eating disorders.

2.2 We hypothesize that the intervention group will have significantly lower levels of perfectionism symptoms than the wait-list control group at post-test. We also hypothesize that the intervention group will have decreased levels of anxiety and depression at post-test than those in the wait-list control group, after controlling for baseline scores.

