### **4.0 Study Endpoints\***

**4.1** The primary endpoint will be scores from the Frost Multi-Dimensional Perfectionism Scale (FMPS)- Concern Over Mistakes Subscale. We will evaluate pre vs post differences. The secondary endpoint will include scores from the Center for Epidemiological Studies Depression Scale (CES-DS), the State-Trait Inventory for Cognitive and Somatic Anxiety (STICSA), the Social Phobia Inventory (SPIN), Eating Attitudes Test (EAT-26), Error Sensitivity Index (ESI), and the Obsessive-Compulsive Inventory- Revised

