## PROTOCOL TITLE: An Exposure-Based Treatment for Perfectionism

psychology department (SONA) or using a brief, 3 question screener that includes three questions from the FMPS-CM. Participants who score a 8 or higher on the screener will be invited to participate in the current study and provided with the study passcode to sign up if they are interested. Additionally, an optional pre-screener not associated with research credit on SONA that includes the same three question screener that is used in the mass screener (3 items from the FMPS-CM) will be available for individuals who would like to participate in the study.

Once they sign up, all participants will be emailed a link to the informed consent form, which will be administered using a Qualtrics survey. All participants must first complete the informed consent before beginning other study procedures. After consenting, the participant will be directed to complete the FMPS. If the participant scores a 29 or lower on the FMPS-CM, they will be given credit for their time (.5 credits) and the experiment will end.

If they score a 29 or above on the FMPS, they will be emailed a link to a HIPAA-Compliant Zoom session scheduled for the appointment time for which they signed up on SONA. The HIPAA-Compliant Zoom meeting will have a waiting room and will be password protected. Participants will be directed to click on the HIPAA-Compliant Zoom link at the time in which their appointment starts. A member of the study team will administer the MINI International Neuropsychiatric Interview (MINI) and the Structured Clinical Interview for the DSM-IV (SCID) Cluster C Personality Disorders Modules via HIPAA-Compliant Zoom. Participants who do not meet inclusion criteria based on this clinical interview will be given .5 credits for their time and the experiment will end.

If participants meet inclusion criteria, they will be randomized to either the intervention group or the wait-list control group. 50% of subjects will be randomized to the treatment group and 50% of subjects will be randomized to the wait list group. Based on that randomization, they will be sent one to two Qualtrics links:

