## **17.0 Data Management\* and Confidentiality**

*17.1 The data analysis plan begins with conducting one-way ANOVAs to assess for baseline group differences. To measure main effects of condition we will use intent-to-treat multiple regression models.*

*17.2 The data will be password protected on an encrypted computer only accessible by the research team. All identifying information will be removed and subjects will be referred to by ID numbers. Consent forms that include subjects' names will be stored separately in a locked filing cabinet in a locked room only accessible to the research staff.*

*17.3 How data will be handled:*

- Information in the data will include an ID number, demographics, information from the clinical interview, and all self-report assessment responses.
- Data will be stored in password-protected files on an encrypted computer that only the study team has access to.
- Data will be stored for a minimum of 4 years after study completion.
- Only members of the study team (i.e., those listed on the IRB submission) will have access to the data.
- The investigator is responsible for receipt or transmission of the data.
- If data needs to be transported, it will be done via password protected files on encrypted computers.

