**25.0 Resources Available**

25.1

- A power analysis based on a repeated measures ANOVA was conducted. The results of this power analysis gave a total sample size of 68 subjects (34 subjects per group). In order to account for attrition, the sample size will be increased to 80 (40 subjects per group).
- The time devoted to this study will last about 1.5 years.
- Baseline and Post-Test assessments will take place in [name] research suite.
- The study team will be thoroughly trained by the investigator before the study begins. We will meet with them individually and review the protocol and consent form. We will provide them with a checklist detailing the steps involved in the study. They will observe a session before conducting one by themselves.

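### No section names baseline FMPS-CM as a covariate in the primary test, and a post-test or change-score test would be less precise than a baseline-adjusted one

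*Combined protocol and SAP*

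**What the plan says.** The primary hypothesis in section 2.2 is: "We hypothesize that the intervention group will have significantly lower levels of perfectionism symptoms than the wait-list control group at post-test". The next sentence of 2.2, on anxiety and depression, adds "after controlling for baseline scores"; the perfectionism sentence has no such phrase.

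Section 4.1 makes the Concern Over Mistakes subscale (FMPS-CM) the primary endpoint and says: "We will evaluate pre vs post differences".

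Section 17.1 is the only analysis plan. After one-way ANOVAs for baseline group differences it says: "To measure main effects of condition we will use intent-to-treat multiple regression models". It names neither the form of the outcome nor any covariate.

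Section 25.1 gives the basis of the sample size: "A power analysis based on a repeated measures ANOVA was conducted". The result is 34 per group, raised to 40 for attrition.

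Section 6.2 sets the order of events. "After consenting, the participant will be directed to complete the FMPS"; the score decides who continues ("If the participant scores a 29 or lower on the FMPS-CM" introduces those who stop); a clinical interview follows; and then "If participants meet inclusion criteria, they will be randomized to either the intervention group or the wait-list control group". So a screening score exists before allocation for everyone randomised. The arm-specific links sent after randomisation ask about perfectionism again, before wait-list participants are told their arm and before intervention participants see the rationale video. That the FMPS is repeated there is an inference from the questionnaire list.

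**The concern.** The two hypotheses in 2.2 sit side by side, and only the secondary one carries baseline control. Read literally, the primary test ignores a score on the same scale that is already in hand for every randomised participant. Section 4.1 points to a change score instead, and 17.1 could be either of these or a model with baseline as covariate. The sections do not choose, and they do not say which score counts as the pre-treatment one.

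What is at stake is precision. With about 34 per arm expected at post-test, a test that makes poor use of the baseline score has a wider confidence interval and less power than these participants could give. An unnamed model also leaves the choice of test open until the data are in.

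**Working it through.** **Inputs from the documents.** 34 per arm after attrition (25.1), two arms at 1:1 (6.1, 6.2), and FMPS completed before randomisation (6.2). The step from 68 to 80 matches 15% attrition, since 68/(1 - 0.15) = 80. The 68 itself cannot be reproduced, because 25.1 gives no alpha, power, effect size or correlation. That is a separate point; only the 34 is used here.

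**Assumptions, none of them in the documents.** Screening score S and post-test score P are normal with unit variance and correlation r before selection. Entry requires S > c, with the cut on FMPS-CM. c runs from 0.5 to 1.0 and r from 0.5 to 0.9. Two-sided 5%.

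**Formulas after selection.** With λ = φ(c)/(1 - Φ(c)):
- var(S) = 1 + cλ - λ²
- Post-test only: var(P) = r²·var(S) + 1 - r²
- Adjusted for S: residual variance = 1 - r²
- Change from S: var(P - S) = 1 - r² + (1 - r)²·var(S)

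The cut against post-test only is r²·var(S)/var(P). The cut against change is (1 - r)²·var(S)/var(P - S).

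**Numbers put in.** For c = 0.5, λ = 1.141 and var(S) = 0.2685. For c = 1.0, λ = 1.525 and var(S) = 0.1991.
- Smallest cut against post-test only (c = 1.0, r = 0.5): 0.25 × 0.1991 = 0.0498; 0.0498/(0.0498 + 0.75) = 6.2%.
- Largest (c = 0.5, r = 0.9): 0.81 × 0.2685 = 0.2175; 0.2175/(0.2175 + 0.19) = 53.4%.
- Smallest cut against change (c = 1.0, r = 0.9): 0.01 × 0.1991 = 0.0020; 0.0020/(0.19 + 0.0020) = 1.0%.
- Largest (c = 0.5, r = 0.5): 0.25 × 0.2685 = 0.0671; 0.0671/(0.75 + 0.0671) = 8.2%.

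**Power at an illustrative 0.6 post-test SD.** Noncentral t with noncentrality 0.6/√(2v/34), where v is the variance relative to var(P); 66 df, or 65 when adjusted. Post-test only has v = 1, noncentrality 2.47 and power 68%.

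| c | r | Cut v post-test only | Cut v change | Power: post-test only | Power: change | Power: adjusted |
|---|---|---|---|---|---|---|
| 0.5 | 0.5 | 8.2% | 8.2% | 68.4% | 68.4% | 72.0% |
| 1.0 | 0.5 | 6.2% | 6.2% | 68.4% | 68.4% | 71.1% |
| 0.5 | 0.9 | 53.4% | 1.4% | 68.4% | 94.3% | 94.6% |
| 1.0 | 0.9 | 45.9% | 1.0% | 68.4% | 90.9% | 91.2% |

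The gain over change is small because the cut shrinks the variance of the screening score, so forcing its slope to 1 costs little.

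**If the cut is not on FMPS-CM.** Section 6.2 stops people at 29 or lower on FMPS-CM but continues those at 29 or above on the FMPS; 10.2 requires at least 29 on the FMPS. These must be reconciled. Without truncation on this subscale, take equal pre and post SDs and correlation ρ of 0.3-0.8. The variance factors are 1 (post-test only), 2(1 - ρ) (change) and 1 - ρ² (adjusted). The cut against post-test only is ρ² = 9-64%. The cut against change is (1 - ρ)/2 = 35-10%. The direction is the same, but the gain over change is larger.

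**The case against.** The strongest reply is that post-test only is the least supported reading. It appears in a hypothesis sentence, not as an analysis. Section 4.1 speaks of change. The repeated measures ANOVA in 25.1 has a group-by-time test that, with two time points, is the change-score test. In 17.1, a regression on arm alone would be simple regression, so the word multiple suggests at least one further term, quite possibly baseline. This largely stands: the large gains arise only against post-test only, and there is no gain if baseline is already in the model. It does not remove the gap, because no section says which term is meant and 2.2 gives baseline control to other outcomes only.

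A second reply is that the correlation is unsupported. That stands too. At r = 0.5 the gain is only 6-8% of variance, so the sign is secure but the size is not. The model also leaves out the earlier three-item screen in 6.2.

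A reader might infer three stronger things, and the documents support none of them:
- That the primary comparison is biased. Randomisation protects all three between-arm tests, and selection on a high score does not change that.
- That the false-positive rate exceeds 5%. That would require running several tests and reporting whichever is significant. No section plans this; the open wording merely fails to rule it out.
- That the trial's power is 68%. That figure belongs to one reading and to an effect chosen for illustration.

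**Conclusion.** The point holds as a gap in specification with a cost in precision. The plan does not name baseline FMPS-CM in the primary test, and the tests that 2.2 and 4.1 describe are less precise than a baseline-adjusted one.

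Under the stated assumptions, adjusting for the screening score cuts variance by about 6-53% against post-test only and about 1-8% against change from screening. Power at 0.6 SD with 34 per arm goes from 68% (post-test only) to about 71-95%. These ranges rest on normal scores, an assumed retest correlation, and an entry cut on FMPS-CM, which 6.2 and 10.2 state inconsistently. The absence of a named covariate is certain; the size of the loss, which may be nil, cannot be fixed from the documents.

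**What to change.** State one primary analysis, in the same terms, in 2.2, 4.1 and 17.1. Suggested wording: *Intent-to-treat linear regression of post-test FMPS-CM on randomised arm and the pre-randomisation screening FMPS-CM; the arm coefficient, two-sided 5%, is the test of efficacy; within-arm pre-post change is descriptive.*

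The screening score is the one to name because it is collected before randomisation from everyone randomised. The later questionnaire score would depend on an FMPS repeat that is only inferred and on both arms completing it before they learn their arm.

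The cost is wording and one degree of freedom, with no new data. The missing inputs of the 25.1 power calculation should be handled as a separate point.

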## 3.0 Background\*

3.1 Perfectionism can be defined as refusing to accept standards less than perfection, or the state of being flawless, sometimes leading to distress and functional impairment (Mirriam-Webster, 1993). The three-component conceptualization was described by Hewitt & Flett (1991) as being self-oriented, being self-critical and holding very high personal standards; socially-oriented, believing that others have incredibly high standards for them; or other-oriented, having extremely high standards of other people. Frost et al. (1990) developed a dimensional model of perfectionism with six parts: (1) excessive concern over mistakes; (2) excessive high personal standards; (3) high parental expectations; (4) parental criticism; (5) exaggerated emphasis on precision, order, and organization; and (6) doubts about actions. The concern over mistakes (CM) dimension is characterized by perceiving errors, even if they are minor, as failure. This can lead to problems like excessive checking, procrastination, reassurance seeking, and distress (Shafran & Mansell, 2001).

The construct of perfectionism can be conceptualized as transdiagnostic with a presence in many disorders, such as obsessive-compulsive disorder, social anxiety disorder, eating disorders, personality disorders, and depression (Egan et al., 2011; Dimaggio et al., 2015). Several studies have reported poorer treatment outcome due to perfectionism (E.g., Elkin et al., 1989; Blatt et al., 1995; Blatt et al., 1998; Zuroff et al., 2000, Shahar et al., 2004; Bizuel et al., 2001). Perfectionism is an important target for treatment as it spans many different disorders and has a negative impact on treatment outcome.

Few treatments have been studied for perfectionism; however, more recently it has gained attention. A mindfulness-based cognitive approach was compared to behavioral self-help for perfectionism by James & Rimes (2017). Participants

## PROTOCOL TITLE: An Exposure-Based Treatment for Perfectionism

were university students high in perfectionism who were randomized to receive either the mindfulness-based cognitive therapy or the CBT self-help therapy. Those in the mindfulness-based cognitive therapy group had significantly lower levels of perfectionism and stress than those in the CBT self-help therapy group. Handley et al. (2015) investigated the effects of group CBT for perfectionism versus wait-list control. Participants who partook in the group CBT had decreased perfectionism as well as reductions in symptoms of anxiety and depression. They also reported increased self-esteem and quality of life. Shafran and colleagues (2017) completed a replication study of a randomized controlled trial of guided internet-based CBT for the treatment of perfectionism, first performed in Sweden. Both studies found significant effects of the treatment on perfectionism, including on the concern over mistakes subscale of the Frost Multidimensional Perfectionism Scale. Another web-based CBT study found significant changes from pre to post-test for perfectionistic concern over mistakes (Radhu et al., 2012).

Exposure therapy is when one is repeatedly exposed to anxiety-provoking stimuli or a feared situation in order to habituate to it so that it no longer leads to significant distress. Though behavioral experiments are described as part of the treatment presented in *When Perfect Isn't Good Enough*, no formal evaluations of pure exposure-based therapy have been conducted to date. This study will expand on the treatment literature in an area that is lacking information. The aim of this study is to develop a novel treatment for perfectionism.

Therapies for many disorders that are associated with those high in perfectionism include an exposure component. An exposure target of perfectionism specifically, however, has not been evaluated.

**3.2** The knowledge gained from this study would add to the existing literature by obtaining information about a potential new computerized treatment for perfectionism. We would like to use an exposure-based intervention because exposure-based treatments have proved beneficial for several disorders, including social anxiety disorder, obsessive-compulsive disorder, and eating disorders (E.g., Bulik et al., 1998; Foa et al, 2005; Rodebaugh et al., 2004), all of which are disorders that overlap with perfectionism (Egan et al., 2011).

### **4.0 Study Endpoints\***

**4.1** The primary endpoint will be scores from the Frost Multi-Dimensional Perfectionism Scale (FMPS)- Concern Over Mistakes Subscale. We will evaluate pre vs post differences. The secondary endpoint will include scores from the Center for Epidemiological Studies Depression Scale (CES-DS), the State-Trait Inventory for Cognitive and Somatic Anxiety (STICSA), the Social Phobia Inventory (SPIN), Eating Attitudes Test (EAT-26), Error Sensitivity Index (ESI), and the Obsessive-Compulsive Inventory- Revised

## PROTOCOL TITLE: An Exposure-Based Treatment for Perfectionism

(OCI-R) to see if there were any decreases from pre to post assessment. An additional secondary endpoint will be group differences on the behavioral tasks.

### 5.0 Study Intervention

- 1.1 Description: Exposure-Based Perfectionism Treatment (EPT) involves repeated engagement in computerized tasks that instruct participants to purposefully make mistakes. There are three main tasks:

Misspelling Task: Participants will be presented with a phrase or a short sentence and be asked to copy that in the text box below. They will also be instructed to spell at least three words wrong in the sentence and then review the text as a whole after making the spelling errors. After they finish, they will click the next button and be given feedback stating that they copied the phrase or sentence incorrectly. This sequence will be repeated using different phrases or sentences, lasting approximately ten minutes total.

Simple Math Task: Subjects are presented with a simple math problem (e.g.,  $5+5$ ) and told to select the answer from the choices below within a 20 second time limit. The response options only include incorrect answers. After selecting a response, a feedback screen will appear stating that their response was incorrect. This sequence will be repeated with different simple math problems (addition, subtraction, multiplication, and division) for a total of approximately 10 minutes.

Shape Ordering Task: Subjects will be presented with a series of eight shapes, each shape lasting 1 second on screen, and be instructed to recall the order in which they were presented after viewing. Participants will be given 20 seconds to decide the order in which they think the shapes are presented before being automatically advanced to the next trial. After each trial they will be given feedback stating that their response was incorrect.

Distress Ratings: Before subjects begin the tasks and after the tasks end, participants will be asked to rate their current and peak levels of distress and frustration. Additionally, participants will rate characteristics of their perfectionism (using questions from the FMPS-CM) before and after the tasks.

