1. Wait List Qualtrics Link: This link will include questionnaires asking about their perfectionism, mood, and behaviors. A detailed list of questionnaires is provided below. After completing questionnaires, participants will be informed that they have been assigned to the wait list control group. They will be asked to complete the post-assessment questionnaires via a link that will be sent to them via email at the start of their post-assessment appointment time, which they signed up for on SONA. Additionally, they will be asked to refrain from seeking treatment for perfectionism for the duration of the study.

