## PROTOCOL TITLE: An Exposure-Based Treatment for Perfectionism

2. Intervention Qualtrics Link: This link will include questionnaires asking about their perfectionism, mood, and behaviors. A detailed list of questionnaires is provided below. After completing questionnaires, participants will be directed to watch a pre-recorded video with study personnel providing information about perfectionism and the rationale of the intervention. They will also be informed that they will be asked to click on a link to complete the first intervention session immediately following this video and complete the intervention at home 4 times: 3, 6, 9, and 12 days after the baseline visit. A Qualtrics link to the first treatment session will be provided on the page after the video.

Those in the intervention group will then complete the first treatment session using the provided link. This will include three tasks, each targeting specific symptoms of perfectionism. Detailed information about the tasks is provided above. At the end of the treatment session, they will be directed to watch a video reminding them that they will receive Qualtrics links 4 times over the next two weeks: 3, 6, 9, and 12 days after the treatment. They will be instructed to complete each treatment session within 24 hours of receiving the link.

The first session will last approximately 45 minutes for those assigned to the wait list and 1 hour and 15 minutes for those assigned to the intervention.

Two weeks later, subjects will receive a Qualtrics link for the post-test assessment, in which the following will occur:

- The participants will be asked to complete questionnaires about their perfectionism, mood, and behaviors.
- Subjects will be debriefed.

Questionnaires:

Frost Multidimensional Perfectionism Scale (FMPS)

MINI International Neuropsychiatric Interview (MINI)

Structured Clinical Interview for the DSM-IV (SCID) Cluster C

Personality Disorder Modules

Eating Attitudes Test (EAT-26)

Center for Epidemiological Studies Depression Scale (CES-DS)

Social Phobia Index (SPIN)

State-Trait Inventory for Cognitive and Somatic Anxiety (STICSA)

Obsessive-Compulsive Inventory- Revised (OCI-R)

Error Sensitivity Index (ESI)

6.3

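### Do in-session ratings that use primary-outcome items, given in the intervention arm only, require a change to the plan?

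*Combined protocol and SAP*

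**What the plan says.** Section 4.1 names the outcome: "The primary endpoint will be scores from the Frost Multi-Dimensional Perfectionism Scale (FMPS)- Concern Over Mistakes Subscale", evaluated before and after. The secondary list in the same paragraph includes "Eating Attitudes Test (EAT-26), Error Sensitivity Index (ESI), and the Obsessive-Compulsive Inventory- Revised".

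Section 5.0 describes three computerised error-making tasks and then, under Distress Ratings, asks for distress and frustration ratings before and after the tasks. It continues: "Additionally, participants will rate characteristics of their perfectionism (using questions from the FMPS-CM) before and after the tasks". It does not say how many items are used or at which sessions.

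Section 6.2 sets out who does what:

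- **Everyone, before randomisation.** Recruitment may use a "brief, 3 question screener that includes three questions from the FMPS-CM". The full scale follows: "After consenting, the participant will be directed to complete the FMPS".
- **Intervention arm.** Participants complete the baseline questionnaires and watch a video, and then "A Qualtrics link to the first treatment session will be provided on the page after the video". They are also told to "complete the intervention at home 4 times: 3, 6, 9, and 12 days after the baseline visit", each session within 24 hours of its link. Post-test follows two weeks after the first session.
- **Wait-list arm.** Participants complete the baseline questionnaires and learn their assignment. The next contact described is the post-test: "They will be asked to complete the post-assessment questionnaires via a link that will be sent to them via email".

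Section 17.1 plans intent-to-treat multiple regression for the effect of condition. Neither that section nor section 4.1 makes any use of the in-session ratings. Section 6.3 places all data collection materials in the appendix of the IRB submission, which is not among the documents reviewed.

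**The concern.** The outcome is self-reported by people who know their assignment. In one arm only, participants hear the treatment rationale, then answer items from the outcome subscale immediately before and after tasks meant to lower those answers, possibly up to a day or two before the final assessment. Familiarity with the items, or a sense of what answer is expected, could shift the post-test score without any change in perfectionism.

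Such a shift would arise after baseline and because of assignment. Neither randomisation nor adjustment for the baseline score would remove it, and it would be counted in the estimated effect of condition. It also looks avoidable, because the exposure tasks do not depend on which items are used as the in-session probe.

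**Working it through.** The plan states no count of rating occasions, so there is no figure to reproduce. The check is a count by arm, followed by a look at what the imbalance can affect.

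**1. Who receives the ratings.** No sentence restricts them to one arm. However, they sit in the intervention section, are timed around the treatment tasks, and are absent from the wait-list steps in section 6.2. Intervention-only is the sound inference.

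**2. Number of extra occasions.** Sessions fall on days 0, 3, 6, 9 and 12, which is 1 + 4 = 5.

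| Reading of section 5.0 | Intervention | Wait-list |
|---|---|---|
| Every session (natural reading) | 5 × 2 = 10 | 0 |
| One session only | 1 × 2 = 2 | 0 |

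A third reading, one rating before the first session and one after the last, also gives 2 against 0. It fits the text less well, since the ratings are described around the tasks.

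**3. Gap from last rating to post-test.** Post-test is on day 14. The day-12 session may be done up to 24 hours after its link, so on day 12 or 13.

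- Every session: 14 − 13 = 1 day to 14 − 12 = 2 days, if sessions and post-test run to schedule.
- First session only: 14 − 0 = 14 days. Both ratings then fall on the baseline day, shortly after the participant has completed the full questionnaires.

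**4. Contact with the items that the arms share before post-test.**

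- Mass screener: 0 or 1.
- Optional pre-screener with the same three items: 0 or 1. Nothing in section 6.2 bars taking both.
- Full FMPS after consent: 1.
- FMPS again in the baseline link, if repeated there: 0 or 1.

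The total is 1 to 4 in each arm. The first three precede randomisation and the fourth is the same in both arms.

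**5. What the ratings can affect.** In the intervention arm the baseline questionnaires come before the video and the first session, so the in-session ratings cannot touch the baseline score. The post-test score comes from a separate questionnaire. An analyst following sections 4.1 and 6.2 would take the pre and post values from those two assessments. Only carry-over into the post-test answers remains, and the documents contain nothing from which its size or sign could be derived. Familiarity or expectation might lower reported concern; repeated attention to mistakes might raise it.

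**6. What replacing the items would achieve.** The count of outcome items would become 0 against 0. One arm would still rate the same construct repeatedly if other error-concern items were used, and it would still have the video, the sessions and the distress and frustration ratings. The Error Sensitivity Index could not be the substitute, because it is itself a secondary endpoint. The trial would lose a within-session measure on the scale of the primary outcome.

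**The case for a change.** The strongest case for a change is that the video, the session contact and the tasks belong to the intervention, whereas the choice of probe items is a measurement decision. A trial resting on one self-reported subscale should not rehearse it in one arm. No stated endpoint or analysis uses these ratings, so swapping a few survey items before enrolment would cost little.

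The distinction is fair, and the imbalance stands as a matter of fact. Two parts of the argument do not carry through.

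- **The gain is not shown.** Removing the items removes item familiarity but leaves repeated self-rating and expectation in one arm. The loss of a process measure on the outcome's own metric is certain, while the benefit is conjecture. Trialists could reasonably choose either way.
- **The low cost applies only before enrolment.** The documents do not give enrolment status, but the revision history runs through five revisions from July 2019 to October 2020, so recruitment may well have started. Changing session content part-way would leave early and late participants with different sessions, which is worse than the imbalance.

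Section 5.0 is also silent on the items and sessions. That is a gap in the text, but the items, and possibly the sessions, may be given in the IRB appendix. Filling it in would alter no estimate.

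**Conclusion.** No change to the plan follows. The arms differ in exposure to the outcome items by 10 occasions against 0 on the natural reading, or 2 against 0 on the narrowest, on top of 1 to 4 contacts common to both. This is an unequal assessment of unknown effect and not a demonstrated bias. It is one of several differences built into an unblinded wait-list comparison. The contrast between the whole intervention package and the wait-list remains estimable, and the planned sample size of 80 does not depend on the point.

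The conclusion assumes that the ratings are given in the intervention arm only, that sessions and post-test keep roughly to schedule, and that the primary scores come from the baseline and post-test questionnaires and not from the in-session ratings. The first and third are the sensible reading of sections 4.1, 5.0 and 6.2. The unequal assessment is worth a sentence when the result is interpreted.
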